We aim to record and collect the following data once weekly on the weekly anniversary of the infantâ€™s first study prone positioning and the date of randomization onto the study for those study participants who were randomized to usual care: transcutaneous CO₂ (TCO₂) if available or PCO₂ from any blood gas, SaO₂ from cardiopulmonary monitors, PaO₂ from arterial blood gases within 1 hour of positional change (if available), ventilator or other respiratory support modality settings and direction of changes within 1 hour of positional change. Specifically, percent change in inspired oxygen, change in ventilator rate (breaths per minute), tidal volume (milliliters), peak inspiratory pressure (cm H₂O), positive end expiratory pressure (cm H₂O) and the number of episodes of oxygen desaturations will be collected. Current comorbidities, most recent chest x-ray findings within a 7day interval will also be documented once weekly.

Other data: duration of time on any respiratory support (days), duration of use of endotracheal tube, non-invasive positive pressure ventilation (NIPPV) and continuous positive airway pressure (CPAP), time to FiO₂ of 21% (irrespective of type of respiratory interface), type of medications to treat BPD (use of oral, inhaled or intravenous postnatal steroids for mitigation of BPD, caffeine, diuretics daily or intermittent), presence of pulmonary hypertension as documented by echocardiogram, use of sedatives and analgesics, pharmacologic treatment of

GERD, use of inhaled nitric oxide on DOL 7 or later. Additionally, the mode of ventilation at 7 days after birth, DOL when maximal feeds achieved (total fluids of 160 milliliters per kilogram per day), DOL at which feeding by mouth was initiated and DOL at which feeds were administered by mouth only, diagnosis of plagiocephaly, and the duration of NICU stay. Demographic data of interest include gestational age at birth (weeks), maternal comorbidities, infant comorbidities, growth status (small, appropriate or large for gestational age), weight at birth (kilograms) and use of antenatal steroids.

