that patient characteristics are distributed similarly across groups. The difference between the intervention and control arms in the rate of BPD at 36 weeks post-conceptional age and other outcomes will be estimated, along with corresponding 95% confidence intervals. In exploratory analyses, the chi-square test will also be applied to assess whether the rates of BPD and other binary outcomes are significantly different between groups, and the two-sample t-test will be used compare the mean values of continuous variables measured at a specific visit. Logistic and linear regression models will also be fit to the data to adjust for any baseline characteristics that are not balanced across groups despite randomization. Weekly physiologic, ventilator and other clinical data will be obtained and analyzed using generalized linear mixed models, with the logit link for binary outcomes and the identity link for continuous outcomes, to account for the correlation in repeated measures from the same infant. Missing data will be handled by analyzing the available data as well as by multiple imputation using chained equations. All analyses will be based on the intent-to-treat approach, and results will be viewed as exploratory and hypothesis generating.

We plan to randomize a total of 60 patients 1:1 to intervention and control (N=30 per arm). Since this is a pilot trial, the goal is to obtain preliminary data on effect sizes. Therefore, formal power calculations were not performed. With 30 patients per arm, the precision, as measured by the width of the 95%CI, with which the true intervention effect (i.e., difference between groups) can be estimated is +/- 25% or better. For example, to gauge the magnitude of the primary outcome of BPD incidence and the potential benefit of standardized prone positioning, we evaluated 2019 BPD rates in our NICU. There were 107 patients described as VLBW at birth. Of those, 34 infants developed moderate to severe BPD, a rate of 31%. If the observed BPD rate is reduced to 21% in the intervention arm for a between group difference of

10%, then the corresponding width of the 95% CI for the true difference will be +/- 22%. We anticipate performing this pilot study over 2-3 years to account for yearly variations in the admission of VLBW patients.

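### Time to FiO2 21% has no rule for infants who never reach it or who die first, so its estimated effect could be biased by an amount, and even in a direction, that the plan does not settle

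*Combined protocol and SAP*

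**What the plan says.** Under Evaluations and measures, the list of other data includes time to FiO2 21% ("irrespective of type of respiratory interface"), days on respiratory support by type, the day of life of feeding milestones, "and the duration of NICU stay". No time origin, end of observation or death rule is attached to any of them. The stop at 36 weeks, discharge or room air in the same section applies to the weekly physiologic and ventilatory data. The limit in the Study plan applies to the positioning itself.

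Statistical Considerations says that differences in BPD and "other outcomes will be estimated, along with corresponding 95% confidence intervals". For continuous outcomes it names a two-sample t-test (for variables measured at a specific visit), linear regression and, for weekly data, mixed models. No time-to-event or competing-risk method appears. On gaps in the data: "Missing data will be handled by analyzing the available data as well as by multiple imputation using chained equations". On the analysis population: "All analyses will be based on the intent-to-treat approach". On purpose: "the goal is to obtain preliminary data on effect sizes". Results are described as exploratory.

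**The concern.** An infant still on oxygen when observation ends has not lost a measurement. The infant was observed not to reach 21%. If the time field is left blank, available-data analysis removes that infant because of something that happened after randomisation, which sits badly with the intent-to-treat statement. Imputation from the other infants supplies a weaning time that contradicts what was seen, and after a death an imputed weaning time has no meaning. If one arm weans more infants, the comparison among those who weaned leaves out that part of the effect.

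Support durations and NICU stay have the opposite defect. They are not blank after a death but cut short by it, so an early death improves the arm's mean.

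At stake is the quality of the effect sizes that the pilot exists to supply. A larger later trial would not remove a bias of this kind, and a rule chosen after seeing the data leaves room for selective analysis.

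**Working it through.** **1. The plan's own figure.** For 31% v 21% with 30 per arm, 1.96 × √(0.31×0.69/30 + 0.21×0.79/30) = 0.221, matching the stated ±22%. At 50% v 50% the half-width is 25.3 points, against a stated 25. Both concern the BPD rate; the plan gives no figure for time to FiO2 21%.

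**2. Inputs.** The documents give no unweaned share, no weaning-time distribution and no expected effect, so everything below is illustrative. Assumed unweaned shares (control v intervention): 31% v 21%, borrowed from the BPD example ("If the observed BPD rate is reduced to 21% in the intervention arm"), and 10% v 6% and 5% v 3%. Assumed window T = 63 days, for example day 7 of an infant born at 26 weeks to 36 weeks: (36 − 27) × 7. Benefit means control minus intervention, in days.

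**3. One distribution per arm.** With unweaned share u and exponential times, λ = −ln(u)/T. The mean with every infant kept (non-weaners at T) is (1 − u)/λ. The mean among weaners only is 1/λ − T·u/(1 − u).

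- Control, u = 0.31: λ = 0.01859; all infants 37.12; weaners only 25.49.
- Intervention, u = 0.21: λ = 0.02477; all infants 31.89; weaners only 23.62.
- Benefit: all infants 5.23; weaners only 1.87. Loss = 1 − 1.87/5.23 = 64%.

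The log-normal case uses the same comparison with SD of log time 0.3 to 1.0, each curve set to the stated share at T. Losses are taken from unrounded values.

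| Unweaned | Exponential: all v weaners | Log-normal, SD 0.3: all v weaners | Range of loss |
|---|---|---|---|
| 31% v 21% | 5.23 v 1.87 | 3.21 v 2.11 | 34–64% |
| 10% v 6% | 3.58 v 1.99 | 3.06 v 2.35 | 23–44% |
| 5% v 3% | 2.55 v 1.70 | 2.55 v 2.13 | 17–34% |

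Imputation that uses arm alone reproduces the weaners-only result. Adding baseline predictors recovers part of the loss, depending on how well they predict weaning time.

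**4. Mixture model.** Let a share p never wean and let weaners average m days. The all-infant mean is p·T + (1 − p)·m. Control: 0.31×63 + 0.69×25 = 36.78. Intervention, with p = 0.21:

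| Weaner mean, intervention | All-infant mean | Benefit, all | Benefit, weaners | Result |
|---|---|---|---|---|
| 15 | 25.08 | 11.70 | 10 | 15% loss |
| 22 | 30.61 | 6.17 | 3 | 51% loss |
| 25 | 32.98 | 3.80 | 0 | 100% loss |
| 28 | 35.35 | 1.43 | −3 | sign reversed |

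At 5% v 3% never weaning, the first two rows give losses of 4% and 18%. Overstatement is also possible. At 50% v 40%, a 49-day window and weaner means of 25 v 15, the all-infant benefit is (0.5×49 + 0.5×25) − (0.4×49 + 0.6×15) = 37.0 − 28.6 = 8.4, against 10 among weaners: 19% too large.

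**5. Against random error.** At 31% v 21% the variances of the capped times are 514 and 490 (exponential), so 1.96 × √((514 + 490)/30) = 11.3 days. For log-normal times with SD 0.7 they are 316 and 330, giving 9.1 days. The corresponding gaps are 5.23 − 1.87 = 3.4 and 5.32 − 3.13 = 2.2 days, well inside those half-widths.

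**6. Deaths and durations.** Background reports 9 deaths among 107 infants, 8.4%. If that rate held after enrolment (an assumption), 60 × 0.084 ≈ 5 deaths would be expected. One death at day 14 in an arm of 30, against an assumed mean of 40 to 60 support days, moves that arm's mean by (14 − 40)/30 = −0.9 to (14 − 60)/30 = −1.5 days.

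**The case against.** A reader might infer that the plan will shrink the weaning benefit by one sixth to two thirds. The documents do not support that. The range comes from models in which one curve per arm ties the speed of weaning to the unweaned share. The mixture in step 4 breaks that tie, and neither size nor direction survives.

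A reader might also take the 31% and 21% as unweaned shares. They are a poor proxy in both directions: Grade 2 BPD includes infants already at 21% FiO2, while Grade 1 infants on low-flow cannula may still be on oxygen and are not counted. The 2019 rate also covers all VLBW infants, not only those still on support at day 7. And if time to 21% is followed to discharge rather than 36 weeks, only deaths and infants discharged on oxygen lack a value, a share that the documents do not give.

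Nor does the plan say that an unreached time is coded as missing. The t-test is worded for variables at a specific visit, and no predictors are listed for the imputation. A strong predictor set could recover much of the loss: with an assumed correlation of 0.9, linear imputation cut it to 14% (exponential) or 2% (log-normal) at 31% v 21%.

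All of this stands and limits the claim. What remains is that no other method is offered for a blank time, and that these infants and any deaths need a rule before the data are seen.

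**Conclusion.** The gap is real and of low severity. If infants who do not reach 21%, or who die first, are left without a time, the named methods select on a post-randomisation outcome or impute a value that contradicts observation. The resulting bias is often toward no effect when treatment both speeds weaning and lowers the unweaned share: 17–64% of the benefit under the single-distribution assumptions. It may instead be negligible, total, an overstatement or a reversal. The documents cannot narrow this. The shortening of support durations and NICU stay by death is a separate, smaller matter.

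It would be wrong to conclude that the trial's main result is compromised. The BPD outcome at 36 weeks and its stated precision are unaffected, these outcomes are exploratory, and the modelled gap of 2.2–3.4 days lies inside a half-width of about 9–11 days.

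**What to change.** In Statistical Considerations:

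- State that not reaching FiO2 21% is an observed outcome, neither missing nor imputed.
- Count from randomisation to one stated end of observation, for example 36 weeks PCA, and keep every randomised infant. Say how infants already at 21% at randomisation are counted.
- Analyse time to FiO2 21% by cumulative incidence with death as a competing event. Alternatively, analyse it and the support durations as days alive and off oxygen, or off support, up to that cap, adjusted for gestational age because the window to 36 weeks differs between infants.
- State how deaths are counted in NICU stay.

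The cost is a few sentences, a little more analysis, and recording dates of death and of any return to oxygen or support. The small downside is that results become capped means or cumulative incidence rather than simple mean days. No extra infants are needed.

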Title: Prone Versus Supine Positioning and the Impact on Bronchopulmonary Dysplasia in Very Low Birth Weight Infants

NCT04890158

IRB Approved: 27-OCT-2021

Title: Standardized prone positioning compared to usual positioning of very low birth weight infants receiving respiratory support and the effect on bronchopulmonary dysplasia (bpd).

Hypothesis: Standardized prone positioning in ventilated, very low birth weight, preterm infants will lead to a reduction in moderate (Grade 2) to severe (Grade 3) BPD as assessed at 36 weeks post conceptional age (PCA).

Background: Bronchopulmonary Dysplasia (BPD) occurs most often in those infants born less than 32 weeks gestation and in those weighing less than 1500 grams at birth. While its definition is somewhat variable, the diagnosis usually rests on the duration of need for oxygen and use of positive pressure ventilation. That is, oxygen use for ≥ 28 days, before 36 weeks PCA or discharge, whichever is earlier, coupled with use of positive pressure ventilation including invasive (via endotracheal tube or tracheostomy tube) as well as non-invasive modalities such as nasal continuous positive airway pressure (NCPAP), non-invasive positive pressure ventilation (NIPPV), nasal cannula (NC) or high flow nasal cannula (HFNC).⁽¹⁾ With three clinical classifications of severity, mild, moderate and severe, we find that 16% of infants in large cohort studies with a weight less than 1000 grams at birth will have severe BPD.⁽²⁾ However depending on the definition of "severe BPD" used, it could encompass up to one third of all premature infants⁽¹⁾. For 2019, The Children's Hospital at Montefiore-Weiler Division Neonatal Intensive Care Unit had 34 of 107 (31.7%) very low birth weight infants (VLBW), i.e those born less than 1500 grams, who were diagnosed with moderate to severe BPD. BPD was defined as utilization of a ventilator or continuous positive airway pressure (CPAP), use of HFNC or regular flow NC >2 L at 36 weeks PCA. Of the 107 VLBW infants identified, 9 died.

There is considerable practice variation in the respiratory management of BPD patients.

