on positive pressure support for at least 7 days after birth AND/OR on any other respiratory device such as nasal cannula with flow rates greater than 2LPM receiving supplemental oxygen of greater than 21% for at least 7 days after birth. Positive pressure for the purposes of this study is defined a nasal cannula delivering a flow of 2 LPM or higher, continuous positive airway pressure (CPAP), non-invasive positive pressure ventilation or non-invasive mechanical ventilation (NIPPV/NIMV), as well infants who are intubated or have a tracheostomy for oxygenation and ventilation related to their lung disease, irrespective of the mode of ventilation. We will exclude infants who were previously on room air without a respiratory device who were intubated for the purposes of surgery and were not receiving respiratory support as defined above prior, those intubated for other airway issues such as tracheal stenosis, broncho- or tracheomalacia, etc and not for the management of BPD. Additional patients to be excluded include those with suspected or proven genetic or other major congenital anomalies that may impact cardiac and lung function including cardiac and lung anomalies, as well as those at the time of enrollment who require surgeries that will impact their ability to be placed in prone positioning (eg gastroschisis, omphalocele, etc).

Patients meeting the aforementioned criteria will be assigned to 1. usual care in which positioning and duration in each position is random per usual nursing routine OR 2. Receive standardized scheduled daily prone positioning starting on day of life 7. As part of normal developmental care, most infants are evaluated and have care rendered (touch-time), if stable, and repositioned at set three-hour intervals to permit uninterrupted sleep and/or rest. The hands-off interval will be maintained throughout the study interval. Infants randomized to the standardized scheduled daily prone positioning will be placed in prone body position for a total of 6 hours daily, that is prone position for 3 hours, followed

by supine positioning for 3 hrs, then placed in prone position for another 3-hour interval. Standardized daily positioning will occur for randomized patients until 36 weeks or discharge whichever is first. If needed, position aids, which are part of the normal care routine in our ICU, may be used to facilitate maintenance of prone or supine positioning.

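### Does the ±22% precision example need redoing because its 31% control rate comes from all VLBW births rather than from infants still on support at day 7?

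*Combined protocol and SAP*

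**What the plan says.** The sample size paragraph of Statistical Considerations fixes the size of the trial: "We plan to randomize a total of 60 patients 1:1 to intervention and control (N=30 per arm"). It describes a pilot without a formal power calculation and gives a general precision statement for 30 patients per arm: the difference between groups "can be estimated is +/- 25% or better".

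A worked example follows. Its control rate is the unit's 2019 experience among 107 infants who were VLBW at birth: "Of those, 34 infants developed moderate to severe BPD, a rate of 31" per cent. If the intervention arm has 21%, a difference of 10 points, "then the corresponding width of the 95% CI for the true difference will be +/- 22" per cent.

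The Background gives the same count, "34 of 107 (31.7%) very low birth weight infants (VLBW), i.e those born less than 1500 grams", and adds: "Of the 107 VLBW infants identified, 9 died".

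The Study plan section describes a narrower group. Infants must remain "on positive pressure support for at least 7 days after birth", or be on another respiratory device with supplemental oxygen for the same period. Among those excluded are infants with "suspected or proven genetic or other major congenital anomalies" that may affect heart or lung function.

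**The concern.** The control rate and the trial population do not match. The 31% has every VLBW birth of 2019 in its denominator, including infants who came off support in the first week and the nine who died. The trial leaves out the first group and any infant who died before enrolment. Under the plan's definition, moderate or severe BPD requires respiratory support at 36 weeks, so an infant who needs none by day 7 is unlikely to become a case. Dropping such infants removes mostly non-cases and should raise the rate. A rate nearer 50% widens the interval, so ±22% may be somewhat optimistic for the infants actually enrolled. It is also the only precision figure tied to the primary outcome.

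The example also treats all 30 randomized infants per arm as having a 36-week outcome. Families may withdraw at any point, and the precision calculation makes no allowance for that. If outcomes were lost, the interval would widen again.

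At stake is whether a reader is given a misleading idea of how precisely this pilot can estimate the effect on BPD.

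**Working it through.** **Inputs from the plan.** 30 per arm; control rate 31% (34 of 107); intervention rate 21%; two-sided 95% interval. The half-width for a difference of two proportions is

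h = 1.96 × √[p₁(1 − p₁)/n + p₂(1 − p₂)/n].

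**1. The plan's example.** 0.31 × 0.69 = 0.2139 and 0.21 × 0.79 = 0.1659, which sum to 0.3798. Then h = 1.96 × √(0.3798/30) = 0.2205, or 22.05 points. The stated ±22% is reproduced. 34/107 is 31.78%, so the printed 31% and 31.7% are truncated. Using 31.8% against 21.8% gives 22.3, which still rounds to 22.

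**2. The general statement.** p(1 − p) is largest at p = 0.5, where it equals 0.25. So for any pair of rates with 30 per arm, h ≤ 1.96 × √(0.50/30) = 0.2530. The ceiling is 25.3 points, which agrees with the stated ±25% after rounding and does not depend on the 31%.

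**3. Direction of the mismatch.** Removing a group from the 107 raises the rate as long as cases make up less than 31.8% of those removed. If the nine deaths were all non-cases (the documents do not say), removing them gives 34/98 = 34.7%. No figure is given for infants off support by day 7 or for those excluded. A higher rate is likely; its size cannot be derived.

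**4. Effect of a different control rate** (assumed rates, 10-point difference, 30 per arm):

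| Control vs intervention | Half-width (points) |
|---|---|
| 31% vs 21% (plan) | 22.05 |
| 35% vs 25% | 23.1 |
| 40% vs 30% | 24.0 |
| 45% vs 35% | 24.7 |
| 50% vs 40% | 25.0 |
| 55% vs 45% | 25.2 |

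Across the table the example moves by about 1 to 3 points, and every value is within ±25% after rounding.

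**5. Effect of lost outcomes** (assumed numbers assessable per arm):

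| Rates | 28 per arm | 27 per arm | 24 per arm |
|---|---|---|---|
| 31% vs 21% | 22.8 | 23.2 | 24.7 |
| 40% vs 30% | 24.8 | 25.3 | 26.8 |
| 50% vs 50% | 26.2 | 26.7 | 28.3 |

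At the plan's own rates the general figure survives a 20% loss (24 of 30). At 40% vs 30% it holds after rounding with 27 assessable. It is passed by more than a point only when losses are combined with rates near 50% in both arms, or when losses reach about 20% at a higher control rate.

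**The case for a change.** The strongest case for a change is that the plan uses the 2019 figures to gauge the primary outcome and the potential benefit, in a pilot meant to yield preliminary effect sizes. A planning rate should then describe the infants to be enrolled. The likely direction of the error follows from the plan's own outcome definition, and two added sentences would cost little. Multiple imputation, which the plan intends alongside an available-data analysis, does not in general restore the precision lost with a missing outcome.

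Most of this stands as description. The populations differ, the enrolled rate is probably above 31%, and the example does equate infants randomized with infants assessed.

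What does not stand is the need to act. The example is worded as a conditional illustration, its denominator is stated openly, and it follows a general figure that covers any control rate. That general figure is itself stated for 30 patients per arm, so its condition is visible. The documents give no loss rate and do not say that a withdrawn infant's outcome is lost, so any reduced number per arm is the reader's assumption. Nor do they show that day-7 support and exclusion status can be retrieved for the 2019 births, so a corrected rate may not be easy to obtain.

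**Conclusion.** No change is needed, because a change would bring no practical gain. The denominator mismatch is genuine, but it touches one correctly computed and openly sourced illustration. With 30 assessable infants per arm and a 10-point difference, a control rate of 35% to 50% would move the half-width from 22.05 to between 23.1 and 25.0 points. The ceiling for any rates is 25.3, so the general ±25% is the figure to rely on, and it is already in the plan.

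The trial's 60 infants, its analysis and its exploratory reading of results do not depend on the 31%. Readers should simply bear in mind that this rate describes all VLBW births and that the enrolled rate may differ.

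This conclusion assumes the usual large-sample interval for a difference in proportions, which reproduces the plan's figure, and few lost outcomes. With 27 or 28 assessable infants per arm, the excess over 25 would be at most 1.7 points, and only with 50% in both arms. The final report's confidence interval will reflect the observed rates and the numbers actually assessed, whatever the planning example said.
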